3.2. SCHEDULE OF VISITS AND PROCEDURES

A schedule of visits and procedures is provided in Table 1.

Table 1: Schedule of Visits and Procedures

Procedures	Baseline	Follow-Ups	Final Evaluation
Study procedures			
Informed Consent and Privacy Authorization	X		
Inclusion/Exclusion Criteria	X		
Demographics			
Age, Race, Gender, Education Insurance Status (from chart)	X		
Marital, Employment, Insurance Status	X		
Medical History			
Height, Weight, Smoking/Tobacco Status	X		
Spinal Cord Injury Information (from chart)	X		
Type of Bladder Management	X		
Number of Concomitant Ulcers	X	X	X
Use of Antibiotics	X	X	X
Primary efficacy endpoint			
Ulcer Depth, Length, Width, Stage	X	X	X
Secondary endpoints			
Wound Infection Status	X	X	X
Amount and Type of Exudate	X	X	X
Color/Type of Tissue/Character of Wound Bed	X	X	X
PUSH Scores	X	X	X
Health Care Resource Utilization (Wound-Related)		X	X
Safety			
Reason for Early Discontinuation (if applicable)		X	
Adverse Events	X	X	X

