 - a. *Determination of study ulcer*: if a patient has multiple Stage III or Stage IV ulcers, the ulcer with the highest total NPUAP PUSH score will be considered the study ulcer for the duration of the study. This is the ulcer that will be treated with Microcyn or saline. The patient and investigator should be encouraged to treat the patient's other wounds in accordance with the randomization scheme. However, the other wounds may be treated in whatever manner the Investigator deems most appropriate. If the other wounds are treated differently from the study ulcer, the Investigator needs to emphasize the importance of adhering to the study protocol at all times for the study ulcer.
 - b. *Location*: Note anatomical location of study ulcer.
 - c. *Debridement*: (yes/no) If in the opinion of the investigator the ulcer requires debridement, Microcyn or saline solution (as per randomization) is to be used during debridement.
 - d. *Size*: (volume) This is the primary endpoint. The wound size should be measured after debridement if debridement is performed. Size will be determined through clinician measurement with photographic documentation.
 - e. *Description*:

1. % Granulation
 2. % Necrosis
 3. % Eschar
 4. % Slough
 5. Purulence
 6. Odor
 7. Stage
 8. NPUAP PUSH 3.0 total and sub-scores
6. Assess for Adverse Events (AEs) before study product application
 7. Apply study product to wound, while simultaneously demonstrating to patient and/or caregiver how to apply study product to wound (see Section 3.2.3) subject and provide written instruction for use. For patients receiving home care services, home care nursing staff will be provided written instructions on use of product as well as identification of study ulcer, if multiple ulcers are present.
 8. Assess for AEs (post-study product application).
 9. Provide study product to the subject to take home in sufficient quantity to last until next clinic visit.
 10. Review Subject Instructions and Subject Restrictions with patient. Patient will be given these instructions to take home for their and their caregivers' reference and review.

3.2.2. ***FOLLOW-UP VISITS (WEEKS 4, 8, 12, 16, 20, 24)***

The following procedures and information will be performed and recorded at the Week 4, Week 8, Week 12, Week 16, Week 20 and Week 24 visits.

1. Obtain information on current antibiotic use
2. Document study pressure ulcer.

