6.3. OVERALL STUDY EVALUATIONS AND MEASUREMENTS

6.3.1. EFFICACY

For the interim analysis, efficacy will be tested via T-tests of percent change in wound size using an intention to treat (ITT) approach as well as a per protocol analysis. For the final analysis, efficacy will be tested via T-tests of percent change in wound size using an intention to treat (ITT) approach as well as a per protocol analysis. Stratification of efficacy results by smoking status and study ulcer Stage will be conducted, although the results are expected to be similar given the stratified randomization.

For the interim analysis and final analyses, secondary analyses will include Kaplan-Meier analysis to estimate time to complete wound closure, and comparisons of infection status of the ulcer. Number and health care resource utilization (wound-related) will be tallied and compared between Microcyn and saline. Other secondary analyses may include linear and logistical regression to estimate the impact of patient characteristics on study endpoints, with special emphasis on variables that affect healing times, such as diabetes. If there are sufficient number of patients with multiple wounds, a mixed effects linear model

will be run, handling the patient as a group that has been randomized to a treatment to determine if there are any spillover effects of treating one wound with Microcyn.

If the interim analysis indicates that the difference in estimated time to complete wound closure between the two populations is 26% or higher at a significance level of $p < 0.05$, the study will be halted early for success.

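### As specified, the spillover mixed model in section 6.3.1 cannot tell spillover from Microcyn applied directly to other ulcers, and no follow-up outcome is required for those ulcers

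*Combined protocol and SAP*

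**What the plan says.** **The analysis.** Section 6.3.1 sets a condition, "If there are sufficient number of patients with multiple wounds, a mixed effects linear model", and then commits to running the model. The patient is the cluster, "handling the patient as a group that has been randomized to a treatment", and the stated aim of the model is "to determine if there are any spillover effects of treating one wound with Microcyn". The section gives no threshold for a sufficient number, no outcome variable and no model terms.

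**The measurements.** With several eligible ulcers, "the ulcer with the highest total NPUAP PUSH score will be considered the study ulcer for the duration of the study" (section 3.2.1). Size, tissue description, stage and PUSH scores are sub-items of the instruction "Document study pressure ulcer" in section 3.2.1, and section 3.2.2 repeats that structure for every follow-up visit. The only row in Table 1 that is expressly about other ulcers is "Number of Concomitant Ulcers", taken at baseline, follow-up and final visits.

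**The treatment of other ulcers.** Section 3.2.1 says the patient and investigator should be encouraged to treat the "other wounds in accordance with the randomization scheme", and then that "the other wounds may be treated in whatever manner the Investigator deems most appropriate".

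**The concern.** A spillover effect is the effect on an ulcer that did not itself receive Microcyn of treating a different ulcer in the same patient. Estimating it needs two things: healing outcomes on non-study ulcers, and a contrast in which those ulcers are not themselves exposed to Microcyn more often in one arm than in the other. The protocol requires no follow-up outcome of this kind, and its treatment rule works against the second condition.

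If the plan is followed, there are two possible results. Either the model has no protocol-required follow-up data for the ulcers it concerns, or it runs on whatever the clinic happens to hold and reports the effect of directly applied product as spillover. The second is worse, because it would support a claim of benefit to wounds not treated with Microcyn when the data may reflect only direct application.

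**Working it through.** The plan states no effect size, power or sample size for this model, and the 80 patients are a convenience sample (synopsis), so there is no figure to reproduce. The check sets the sections side by side and then uses a simple illustration.

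**1. Outcome data on other ulcers.**
- *Baseline:* choosing the study ulcer by PUSH score implies that every Stage III/IV ulcer is scored once.
- *Follow-up:* section 3.2.2 lists size, description, stage and PUSH under the study ulcer only. Table 1 adds the number of concomitant ulcers. No follow-up size or healing outcome is required for any other ulcer.

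**2. Record of what was applied to other ulcers.** Section 3.2.2 asks about medication under resource use, at patient level. Section 8.1 lists study product administration among the contents of the subject file, without saying by ulcer. Section 7.3 keeps no special record of amounts shipped or dispensed. No per-ulcer product field is specified.

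**3. What the arm contrast would estimate if outcomes existed.** Let
- s = true spillover onto other ulcers in the Microcyn arm that do not receive Microcyn;
- D = total effect on an ulcer that does receive Microcyn, taken as equal in both arms;
- p1, p0 = share of other ulcers given Microcyn in the Microcyn and saline arms.

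If the remaining treatments perform equally in both arms, the contrast in other ulcers is

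p1·D + (1 − p1)·s − p0·D.

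With s = 0 this is (p1 − p0)·D = f·D, where f is the between-arm difference in use. Microcyn use on other wounds in the saline arm lowers f.

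**4. Numbers.** The documents give neither D nor f; both are assumptions. With D = 15 percentage points and s = 0:

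| f | apparent spillover (points) |
|---|---|
| 0.25 | 0.25 × 15 = 3.75 |
| 0.50 | 0.50 × 15 = 7.5 |
| 0.75 | 0.75 × 15 = 11.25 |
| 1.00 | 1.00 × 15 = 15 |

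**5. Does the random patient effect remove this?** No. Mixed models with a random patient intercept were fitted to simulated data: 80 patients, two ulcers each, D = 0.5 SD, s = 0, no Microcyn on other ulcers in the saline arm, 150 runs per setting. The mean apparent spillover was −0.03 SD at f = 0, 0.24 SD at f = 0.5 and 0.48 SD at f = 1 (Monte Carlo standard error about 0.02). The values f·D are 0, 0.25 and 0.50. The random effect handles correlation within patients; it does not separate direct effect from spillover.

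**6. Precision.** Suppose 20%, 40% or 60% of the 80 patients have one further ulcer (assumed, 1:1 allocation), giving 8, 16 or 24 per arm. The difference detectable with 80% power at two-sided 5% is (1.960 + 0.842) × √(2/n) SD = 1.40, 0.99 or 0.81 SD. Even a well-defined version would detect only large effects.

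**The case against.** The strongest reply is that this is a conditional secondary analysis with no decision attached, and that with wound-level data the model has a valid target. Section 6.3.1 treats the patient as the randomised group, so comparing arms across a patient's ulcers is a randomised comparison. This stands. Given the data, the defect is the label and the claim it invites, not the mixed model, and the fix builds on that.

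Several stronger readings are tempting, but the documents do not support them.
- *Other ulcers are not measured at all.* A baseline PUSH score is implied, and a count is taken at visits. The Table 1 row for dimensions and stage is not itself limited to the study ulcer, although it sits under the primary endpoint and the visit instructions tie it to that ulcer. The clinic's usual forms (section 8.1) may also hold something. What can be said is that the protocol requires no follow-up size or healing outcome for them.
- *The product used on other ulcers is recorded nowhere.* The medication question and the subject file may capture some of it. What is missing is a specified field by ulcer.
- *An arm difference would be mostly direct effect.* The share of other ulcers given Microcyn is unknown: use is encouraged, not required, and other treatments are allowed in both arms. The documents support mixing, not its proportion.
- *Restricting to other ulcers that did not receive Microcyn would isolate spillover.* In an open-label trial that choice is made after randomisation, so the subset is selected and the comparison is no longer protected by randomisation.

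**Conclusion.** The point holds in a limited form. As specified, the model cannot identify the spillover effect that section 6.3.1 names. The protocol requires no follow-up outcome for non-study ulcers, and the rule for treating those ulcers lets direct effect and spillover mix with no per-ulcer record to separate them.

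The size depends on two unknowns. The 3.75 to 15 point range illustrates the mechanism and does not predict this trial's result; it rests on zero true spillover, D = 15 points, f between 0.25 and 1.0, and equal performance of the other treatments in both arms. At f = 0 the bias disappears.

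A reader might infer that the trial's main result is compromised. It is not: the primary t-test of percent change in wound size does not use this model, and neither the Kaplan-Meier analysis nor the safety analysis depends on it. The matter is still worth correcting, because the stated analysis can lead to a wrong conclusion and visits that pass without recording cannot be recovered.

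**What to change.** Choose one of two changes in section 6.3.1.

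1. **Delete the spillover sentence.** This costs nothing beyond the amendment.
2. **Keep the model and change its target.** Replace "to determine if there are any spillover effects of treating one wound with Microcyn" with: to estimate the effect of arm assignment on all of the patient's Stage III/IV ulcers, using a mixed model with a random patient effect; this analysis does not separate direct effect from spillover. Then add to sections 3.2.1 and 3.2.2, for each other Stage III/IV ulcer at each visit, the length, width, depth and product used. The cost is some extra recording time for patients with several ulcers, and it works only if adopted prospectively.

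Under either option, make no spillover claim from the subset of other ulcers that did not receive Microcyn. The treatment provision for other wounds in section 3.2.1 and the aim in section 6.3.1 must be reconciled; how those wounds should be treated is not a matter for this review.

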Name of Sponsor/Company:	Oculus Innovative Sciences, Inc.
Name of Finished Product:	Microcyn [®] Skin and Wound Care with preservatives (“Microcyn”)
Name of Active Ingredient:	N/A
Safety Evaluations:	
Adverse Events (AEs) will be recorded at Baseline (pre- and post-application) and at each study visit.	
Efficacy Evaluations:	
Primary Endpoint: The primary endpoint is pressure ulcer size (length, width, depth via clinician measurement with photographic documentation). Secondary Endpoints: Secondary endpoints include healing progress, as measured through the NPUAP PUSH Tool, Version 3.0, time to complete wound closure, infection status of the ulcer including signs/symptoms of infection, amount and type of exudates, color and type of tissue/character of the wound bed, health care resource utilization (wound-related), and adverse events.	
Diagnosis and Main Eligibility Criteria:	
Inclusion Criteria:	

 – Written informed consent including authorization to release health information – Male or female (non-pregnant/nursing) outpatients over the age of 18 – Spinal cord injured – One or more Stage III or Stage IV pressure wound located anywhere on the body – Willing and able to fulfill all obligations of the study, including attending all study visits and has the ability him/herself or via a caregiver to apply study product twice daily 	
Exclusion Criteria:	

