The sample is a convenience sample of 80 patients.	

LIST OF ABBREVIATIONS AND DEFINITIONS OF TERMS

Abbreviation	Definition
AE	Adverse Event
ASIA	American Spinal Cord Injury Association
CFR	Code of Federal Regulations
CTEP-	Cancer Therapy Evaluation Program – Common Terminology Criteria for
FDA	Food and Drug Administration
GCP	Good Clinical Practices
HHS	Health and Human Services
ICH	International Conference on Harmonisation
IEC	Independent Ethics Committee
IRB	Institutional Review Board
ITT	Intention To Treat
MedDRA	Medical Dictionary for Regulatory Activities
NPUAP	National Pressure Ulcer Advisory Panel
PUSH	Pressure Ulcer Scale for Healing
SAE	Serious Adverse Event
SAS	Statistical Analysis Software
SOP	Standard Operating Procedure
UPT	Urine Pregnancy Test
US	United States
WOCBP	Woman of Childbearing Potential

COVER PAGE ERROR! BOOKMARK NOT DEFINED.

SIGNATURE PAGE 2

INVESTIGATOR'S AGREEMENT 3

PROTOCOL SYNOPSIS..... 4

LIST OF ABBREVIATIONS AND DEFINITIONS OF TERMS..... 9

1. INTRODUCTION AND BACKGROUND..... 12

 1.1. STUDY RATIONALE 15

 1.2. DOSE RATIONALE 16

 1.3. STUDY OBJECTIVE..... 16

 1.4. CLINICAL HYPOTHESES..... 16

2. STUDY DESIGN..... 17

 2.1. OVERALL DESIGN..... 17

 2.1.1. *Structure*..... 17

 2.1.2. *Duration* 17

 2.1.3. *Controls*..... 17

 2.1.4. *Dosage/Dose Regimen*..... 17

 2.2. TEST ARTICLE 17

 2.3. STUDY POPULATION 17

 2.4. ELIGIBILITY CRITERIA..... 17

 2.4.1. *Informed Consent and Authorization to Release Health Information*..... 17

 2.4.2. *Inclusion Criteria*..... 19

 2.4.3. *Exclusion Criteria*..... 19

3. STUDY PROCEDURES AND METHODS..... 21

 3.1. SUBJECT ENTRY PROCEDURES..... 21

 3.2. SCHEDULE OF VISITS AND PROCEDURES 21

 Table 1: Schedule of Visits and Procedures 21

 3.2.1. *Baseline Visit* 21

 3.2.2. *follow-up visits (Weeks 4, 8, 12, 16, 20)*..... 24

 3.2.3. *subject application instructions*..... 26

 3.2.4. *subject restrictions* 26

 3.2.5. *Discontinuation/Withdrawal Procedures*..... 26

 3.3. VARIATION FROM SCHEDULED VISIT DAYS..... 27

 3.4. SAFETY ASSESSMENTS 27

 3.4.1. *adverse events*..... 27

 3.5. EFFICACY ASSESSMENTS..... 27

 3.5.1. *Time to wound closure*..... 27

 3.6. SCREEN FAILURES..... 27

 3.7. PROTOCOL DEVIATIONS..... 28

4. PROHIBITED MEDICATIONS AND TREATMENTS..... 29

Table 2: Prohibited Medications and Treatments	29
5. EVALUATION OF ADVERSE EVENTS.....	30
5.1. DEFINITIONS.....	30
5.1.1. Adverse Event Severity Grades	32
5.1.2. Study product Causality	33

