The numbers above represent “nodes” of care with nodes 1-4 representing the four basic components of an effective pressure ulcer care plan: (Node 1) necrotic tissue debridement; (Node 2) initial wound cleansing and repeated cleansing with each dressing change; (Node 3), prevention, diagnose and treatment of infection; and (Node 4), using a wet ulcer dressing that keeps surrounding tissue dry. Nodes 5-14 as shown above represent

assessment and reassessment of the healing strategy and its outcome(s) to ensure optimal healing.

Spinal cord injured patients are an especially vulnerable population for pressure ulcers because of both the immobility rendered by resultant paralysis and of impaired sensation. The National Spinal Cord Injury Statistical Center (NSCISC) estimates that between 231,000 and 311,000 Americans are living with a spinal cord injury (SCI), with approximately 12,000 new cases each year.⁴ As a result of increased research and interest, remarkable progress has been made in improving the quality of life and life expectancy for SCI patients. Secondary complications, however, continue to challenge individuals living with SCI and their caregivers. Pressure ulcers, in particular, “remain the single most important medical complication in terms of loss of time in educational or vocational pursuits, increased hospital stay and resulting financial expenditures.”⁵ In patients with paraplegia, pressure ulcers are the leading cause of rehospitalization;⁶ across injury levels, sepsis from pressure ulcers and genitourinary tract infections are the leading cause of death in Veterans with SCI.⁷

Recent cost estimates on treating pressure ulcers in SCI patients indicate a range of \$2,000 to \$70,000 per wound, with an annual aggregate cost of approximately \$2.2 to \$3.6 billion in the United States alone.⁸ In a retrospective study reviewing medical records of veterans with spinal cord injury, it was found that over 50% of pressure ulcers did not fully heal over the three-year study period, with over 70% of Stage IV ulcers remaining unhealed despite surgeries and multiple hospitalizations.⁹

⁴ *Spinal Cord Injury Facts and Figures at a Glance*, National Spinal Cord Injury Statistical Center, Birmingham, Alabama, February 2010, <https://www.nscisc.uab.edu>.

⁵ Jackson, AB., *Secondary Conditions of Spinal Cord Injury*, Spinal Cord Injury Network, <http://www.spinalcord.uab.edu/show.asp?durki=32106>.

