1.3. STUDY OBJECTIVE

The primary objective is to compare percentage change in wound size in patients with at least one Stage III or Stage IV pressure ulcer in subjects treated with Microcyn versus saline.

The secondary objective is to compare other indicators of wound healing such as time to complete wound closure, elimination of signs of wound infection and to investigate the impact of treatment with Microcyn on subject health care resource utilization (wound-related).

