6. STATISTICAL ANALYSIS

6.1. GENERAL CONSIDERATIONS

All statistical programming will be performed using SAS version 9.1 or higher, or similar statistical program. Statistical significance will be based on two-sided tests at the 5% level of significance. There are two planned analyses. The first will be conducted when the greater of 20 patients or those enrolled in the two (2) weeks following enrollment of the first participant have completed the Week 12 assessments. The second will be when all 80 patients have completed the Week 24 (Final Evaluation) assessments.

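### The interim success stop uses a secondary endpoint at an unadjusted p < 0.05 after about 20 of 80 patients, with no alpha set aside and no role for the primary endpoint

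*Combined protocol and SAP*

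**What the plan says.** Section 6.1 sets one significance level for everything: "Statistical significance will be based on two-sided tests at the 5% level of significance. There are two planned analyses". The first analysis takes place when the greater of 20 patients, or those enrolled in the first two weeks, have completed Week 12. The second takes place when all 80 have completed Week 24.

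The primary objective (Section 1.3) is percent change: "The primary objective is to compare percentage change in wound size". The synopsis places closure time among the secondary endpoints: "Secondary endpoints include healing progress, as measured through the NPUAP PUSH Tool, Version 3.0, time to complete wound closure".

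Section 6.3.1 tests the primary at the interim ("For the interim analysis, efficacy will be tested via T-tests of percent change in wound size") and again at the final analysis, and it treats closure as secondary ("secondary analyses will include Kaplan-Meier analysis to estimate time to complete wound closure"). Its last paragraph then bases the success stop on closure alone, with a p-value threshold of 0.05. The trigger is worded as a "difference in estimated time to complete wound closure between the two populations is 26% or higher at a significance level of" that size.

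The sample size has no power basis: "The sample is a convenience sample of 80 patients". The only information on closure is a veterans' record review cited in Section 1, in which "over 50% of pressure ulcers did not fully heal over the three-year study period, with over 70% of Stage IV ulcers remaining unhealed".

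**The concern.** Four things are wrong with the rule as written.

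1. The trial can be declared a success and ended on a secondary endpoint, whatever the primary shows.
2. There are two routes to a success claim, each at 5%, and no boundary, split or hierarchy links them.
3. The 26% clause has no defined scale. Section 6.3.1 ties the estimate to Kaplan-Meier but does not say whether 26% refers to medians, to restricted means (and to what time) or to closure rates.
4. No test and no direction are named. The word success and Section 1.4 imply benefit of Microcyn, so direction is a wording gap, but the sentence as written counts a difference either way.

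At stake are the trial's chance of a false success claim, an exaggerated closure effect from very few events, and a primary question left largely unanswered.

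**Working it through.** The plan has no alpha or power calculation to reproduce, so the check starts from its design inputs.

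**Interim size.** Eighty patients in up to two years (Section 2.1.2) is 80/104 = 0.77 per week, or about 1.5 in two weeks, so 20 is the binding number. Enrolled when the 20th reaches Week 12: 20 + 12 × 80/104 ≈ 29. No allocation ratio is stated; 1:1 is assumed, giving 10 per arm.

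**Simple reference.** Two independent tests at 5%: 1 − 0.95² = 9.75%. With correlation 0.5 between the two statistics: 9.1%.

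**Does the 26% clause bind on a rate scale?** With 1:1 allocation, closures needed before a given rate ratio reaches p = 0.05 are 4 × (1.96/ln ratio)².
- Time 26% shorter: 4 × (1.96/ln(1/0.74))² = 169.
- Time 26% longer: 4 × (1.96/ln 1.26)² = 288.

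Both exceed 80 patients. Conversely, the smallest observed ratio that gives p < 0.05 is exp(2 × 1.96/√d): 5.8 with 5 closures, 3.5 with 10, 2.4 with 20. On this scale p < 0.05 always implies more than 26%. On a median or restricted-mean scale the clause can bind.

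**Likely closure rate.** At a constant rate, 50% unhealed over three years (156.5 weeks) gives 1 − 0.5^(12/156.5) = 5.2% closed by Week 12. For Stage IV, 1 − 0.7^(12/156.5) = 2.7%. Because more than 50% and 70% stayed unhealed, these are upper limits. The extrapolation is rough, so a range is shown.

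**Chance under no effect of a stop or a significant final primary test** (%, two-sided). Simulation of 20,000 trials per cell, Monte Carlo SE about 0.15-0.2 points. Assumed: exponential closure times, log-rank test, latent correlation 0.5 between closure time and percent change, final t-test on 40 per arm. Follow-up is cut at Week 12 or runs to the interim date (at most 24 weeks).

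| Closed by Week 12 | 5% | 10% | 20% | 30% | 50% |
|---|---|---|---|---|---|
| p alone, Week 12 cut | 5.2 | 5.6 | 8.1 | 9.5 | 9.6 |
| p alone, to interim date | 6.0 | 7.7 | 9.5 | 10.0 | 10.5 |
| plus 26% restricted-mean difference, Week 12 cut | 5.2 | 5.1 | 6.4 | 8.1 | 9.2 |
| plus 26% restricted-mean difference, to interim date (24 weeks) | 5.5 | 6.4 | 8.7 | 9.8 | 10.5 |

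With follow-up to the interim date but the mean restricted to 12 weeks, the figure is about 6-7% at 20-30% closure. If both medians must be reached and differ by 26%, it is 4.7-5.3%, except 8.5% at 50% closure with follow-up to the interim date. If one reached median is enough, it is 4.9-9.5% (Week 12 cut) or 5.4-10.5% (interim date). Counting only results in favour of Microcyn, the range is about 2.3-5.4% against a nominal 2.5%.

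**What a stop would look like if Microcyn works.** Take closure time truly 26% shorter (rate ratio 1/0.74 = 1.35), p alone, saline closure 5-50% by Week 12, 60,000 trials per cell. The stop fires in Microcyn's favour in 0.2-7.7% of trials (Week 12 cut) or 1.1-9.0% (interim date). At those stops the median estimated ratio is 3.8-9.2, from a median of 4-15 closures. Of all stops, 7-27% favour saline.

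**Primary comparison after a stop.** Power of a two-sided 5% t-test from the noncentral t distribution. The documents give no effect size, so these are assumptions.

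| Assumed effect | 10 per arm | 14 and 15 | 40 per arm |
|---|---|---|---|
| 0.63 SD | 27% | 37% | 79% |
| 0.5 SD | 18-19% | 25-26% | 60% |

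**The case against.** The strongest reply concerns size. The only closure data in the documents imply at most about 5% closed by Week 12. There the stop almost never fires and the error is 5.2-6.0% on p alone; nothing in the documents supports 30-50% closure. The median is also a natural Kaplan-Meier summary, and if both medians must be reached the inflation nearly vanishes. In addition, the figures pool two endpoints: the stop does not raise the false-positive rate of the final primary test itself. Finally, the synopsis places the full analysis after all subjects complete their final evaluation, which leans towards following all of the roughly 29 enrolled.

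Much of this stands. A doubling is not established as the likely case. The pooled figure is the chance of either success claim, not the primary test's own error. The stop rates at a true ratio of 1.35 use p alone, and adding the 26% condition can only make stops rarer.

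It does not rescue the rule. The plan never chooses the median reading, so that protection is not pre-specified, and the synopsis sentence does not address a stop. If closures are rare, the rule rarely fires and deleting it loses little; if they are common, the error approaches double. The endpoint mismatch holds in either case.

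**Conclusion.** The concern holds and should be fixed before the interim. The plan, followed as written, requires a stop on a secondary endpoint at an unadjusted 5% and keeps the full 5% for the final primary test.

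The size of the error inflation is uncertain: close to nil at about 5% closure by Week 12, and up to about a doubling at 30-50%, depending on how the 26% is read and how long patients are followed. This rests on 1:1 allocation, exponential closure times, a log-rank test and the assumed correlation.

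The firmer harm does not depend on the inflation. A stop would rest on few closures with an exaggerated estimate. It would leave the primary comparison with 10 per arm, or 14 to 15 if everyone then enrolled is followed.

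**What to change.** **Preferred.** Delete the last paragraph of Section 6.3.1. Add to Section 6.1: *No efficacy stopping is planned. Interim efficacy results are descriptive. The primary endpoint is tested once, at the final analysis, at two-sided 0.05.* Change the interim t-test sentence in Section 6.3.1 to a summary of percent change by arm.

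**If an efficacy stop is kept.** Base it on intention-to-treat percent change in wound size at Week 12, in Microcyn's favour, with a named test and alpha split to total at most 0.05, for example two-sided p < 0.001 at the interim and 0.049 at the final. State which patients the intention-to-treat set contains, since the synopsis and Section 6.2 define the efficacy population differently. State also whether patients already enrolled at a stop are followed to Week 24 for the primary analysis.

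**Cost.** One deleted paragraph and two or three edited sentences. Early stopping for efficacy is given up, or with the 0.001 example becomes very unlikely: about 2% at an assumed 0.63 SD and 8.5% at an assumed 1.0 SD, with 10 per arm. Final power is almost unchanged: 79.2% at 0.049 against 79.5% at 0.05 (0.63 SD, 40 per arm).
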